9.7.6.2. Sensitivity analysis on bleeding outcomes

A sensitivity analysis will be conducted by applying a more restrictive definition to the bleeding diagnoses reported only as main/primary diagnosis during hospitalization, excluding secondary diagnostic codes.

9.7.6.3. Sensitivity analysis on VTE outcome

A sensitivity analysis will be conducted by applying a more restrictive definition to the VTE outcome diagnoses reported only as main/primary diagnosis during hospitalization, excluding secondary diagnostic codes.

9.7.7. Subgroup analysis

A subgroup analysis for primary and secondary outcomes will be performed by age of children at index date (<6 months and 6 months to <2 years).

9.7.8. Combined analysis across data sources

In addition to separate analysis in each data source, descriptive analyses combining cumulative aggregated data of each individual data source will be conducted when possible.

According to GDPR, values must be suppressed whenever a patient count is less than a defined threshold: less than five cases/observations in the Nordic countries, less than six in Spain, and less than ten in France.

Therefore, combined analyses should be possible for characteristics of patients and drug use patterns. However, due to the small sample size and rarity of the outcomes bleedings and recurrent VTE, it is expected that these analyses should only be feasible in the SNDS, in which case combined analyses of outcomes across data sources would not be possible.

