9.2.3. Selection criteria

9.2.3.1. Inclusion criteria

Participants are eligible to be included in the study only if all of the following criteria apply:

- Evidence of initiation of an anticoagulant therapy (index drug), either rivaroxaban oral suspension or other anticoagulation therapies (heparins, VKAs, other DOACs). Initiation will be defined as a first record of any anticoagulation therapy (rivaroxaban or SOC) without any anticoagulation therapy in the previous 6 months, or since date of birth for children less than 6 months (see codes for anticoagulant drugs in [Annex 3](#)).
- Evidence of a prior VTE diagnosis (index VTE), defined as the presence of at least one primary/main or secondary diagnosis code for VTE recorded in inpatient setting in the previous 30 days (see preliminary list for VTE codes in [Annex 3](#)).
- Age less than two years on index date.
- Baseline period for availability of patient data history in the data source. A minimal baseline period of six months before index date for children aged between six months and two years, and a baseline period since birth for children less than six months of age will be required.

According to its indication, rivaroxaban oral suspension should be used after at least five days of initial parenteral anticoagulation treatment. In order to describe the actual clinical practice in real world settings, there will no requirement on this initial parenteral anticoagulation treatment to include patients in the study population, so patients will be identified independently of this. In theory, all patients receiving rivaroxaban should be switchers. In practice, they may appear as initiating directly with rivaroxaban: the observed initial anticoagulant therapy might be different from the actually received initial therapy, if patients have switched drug during hospital stay and if inpatient drug data is not captured. Depending on availability of inpatient drug data in each data source, the observed initiation of the anticoagulant therapy will be identified either in outpatient or in inpatient setting, as shown in [Figure 2](#) below (see [Section 9.4](#)).

SOC for treatment of VTE in children usually include UFH, LMWH and VKA and may vary across countries. With other DOACs receiving indication for VTE in paediatrics, SOC may also evolve over time.

Figure 2 Visualization of patient journey

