9.3.2.2. Secondary outcomes

9.3.2.2.1. Time trends in patient characteristics and anticoagulation treatment patterns

Description by calendar year of:

- Age group at index date
- Medical history at index date
- Class of anticoagulation therapy at initiation

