9.7.2. Patient characteristics

The impact of inclusion and exclusion criteria on the number of patients in the study population will be described in an attrition diagram or table.

The study population will be described according to the descriptive variables mentioned in [Section 9.3.2.1.1](#).

For each exposure category (rivaroxaban and SOC), analyses of patient characteristics will be described, with stratification on the status of exposure, i.e., initiators versus switchers.

Patient characteristics will also be described over time during the study period to identify potential time trends (secondary objective).

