9.9. Limitations of the research methods

The use of secondary data that has not been primarily collected for research purposes comes with specific limitations.

Selection bias

- All patients fulfilling eligibility criteria will be included in the study. The data sources in the different countries differ in terms of contents and expected coverage. Most have a national coverage, while SIDIAP which only covers ~75% of Catalonia is also considered representative of the Spanish population. Therefore, the selection bias is considered to be low with respect to the target countries.

Information bias

- Exposure data
 - Anticoagulation therapy is expected to be initiated during hospital stay and renewed for outpatient use. According to its indication, rivaroxaban oral suspension should be used after at least five days of initial parenteral anticoagulation treatment. Thus, in theory, all patients receiving rivaroxaban should be switchers from parenteral anticoagulant treatment. In practice, the capacity to observe the actual initial parenteral anticoagulation treatment and its duration will depend on the availability of inpatient drug data in the selected data sources. This will be feasible when

inpatient drug data is captured, e.g., in the Danish SMR (soon available, with data collected since May 2018) and in SIDIAP through linkage with hospital dispensation medication. However, inpatient drug data is not captured in SNDS and in Swedish national registers, which represents a risk of exposure underestimation. In this latter situation, the information on anticoagulation therapy and its duration will be based on outpatient prescriptions only, at a time when patients may have already, or not yet, stopped the initial parenteral anticoagulation treatment, and switched to maintenance therapy like rivaroxaban. Hence, when patients will have switched to rivaroxaban during hospital stay in an unobservable period in the data source, they will appear as initiating anticoagulation therapy with rivaroxaban, and not switchers. To avoid immeasurable time bias, the index date will be the first observed record of anticoagulation therapy in each data source, whether it occurs during inpatient stay or afterwards.

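### Section 9.7.8 would combine index therapy and initiator/switcher status across sources that define the index drug differently, because only two of the four record inpatient drugs

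*Protocol*

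**What the plan says.** On pooling, section 9.7.8 states that "descriptive analyses combining cumulative aggregated data of each individual data source will be conducted when possible". After listing the suppression thresholds (below five in the Nordic countries, six in Spain, ten in France) it concludes that "combined analyses should be possible for characteristics of patients and drug use patterns". It sets no other condition. The abstract also lists both topics under combined analyses.

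On the index, section 9.2.3.1 says that, depending on which drug data a source holds, "the observed initiation of the anticoagulant therapy will be identified either in outpatient or in inpatient setting". Section 9.9 gives the rule: "the index date will be the first observed record of anticoagulation therapy in each data source, whether it occurs during inpatient stay or afterwards".

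On which sources see hospital drugs, section 9.9 names the Danish hospital medication register and, by linkage, SIDIAP. It then says that "inpatient drug data is not captured in SNDS and in Swedish national registers". Footnote a of Table 4 draws the same line: Denmark and SIDIAP are marked as including in-hospital treatment, SNDS and Sweden are not. Of a child in SNDS or Sweden who is moved to rivaroxaban before discharge, section 9.9 says: "they will appear as initiating anticoagulation therapy with rivaroxaban, and not switchers".

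The index feeds several planned outputs. Section 9.3.2.1.2 lists index therapy with its duration, switching, and the number and order of agents. Section 9.7.2 describes characteristics by exposure category "with stratification on the status of exposure, i.e., initiators versus switchers". Section 9.3.2.2.1 tracks "Class of anticoagulation therapy at initiation" by calendar year.

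**The concern.** The index drug, and whatever is derived from it, has one meaning where hospital drugs are recorded and another where they are not. Take a child given heparin in hospital and moved to rivaroxaban before discharge. In Denmark this child is recorded as a switcher with two agents. In France the same child is an initiator with one agent and no switch. Adding the two gives a figure that is neither the first treatment received nor the first outpatient treatment.

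Section 9.9 explains this source by source, but section 9.7.8 does not take it up. The exposure sensitivity analysis in section 9.7.6.1 deals with carry-over after a switch, not with unseen hospital treatment. At stake is what the combined tables can say about initial therapy and about how children come to rivaroxaban.

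**Working it through.** **Inputs.** Table 6, average estimates, children with VTE / rivaroxaban users: SNDS 650 / 219, Sweden 98 / 33, Denmark 52 / 18, SIDIAP 45 / 15, overall 846 / 285. Yearly market shares (section 9.5.2): 10%, 32%, 38%, 42%, 50%, 30%. Inpatient drug capture: section 9.9 and Table 4, footnote a.

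**Step 1: reproduce the plan's counts.** Mean share = (10 + 32 + 38 + 42 + 50 + 30)/6 = 33.67%.

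| Source | Children × 0.3367 | Table 6 |
|---|---|---|
| SNDS | 218.8 | 219 |
| Sweden | 33.0 | 33 |
| Denmark | 17.5 | 18 |
| SIDIAP | 15.2 | 15 |
| Overall (846) | 284.8 | 285 |

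The counts reproduce. The four sources sum to 845 children against 846 in the table, which is rounding.

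**Step 2: split by inpatient drug capture.**

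- With capture (Denmark + SIDIAP): 52 + 45 = 97 of 845 children (11.5%); 18 + 15 = 33 of 285 rivaroxaban users (11.6%).
- Without capture (SNDS + Sweden): 650 + 98 = 748 of 845 (88.5%); 219 + 33 = 252 of 285 (88.4%).

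The split hardly moves with the scenario. The no-capture share of rivaroxaban users is 93/106 = 87.7% on the lowest estimates and 410/464 = 88.4% on the highest.

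**Step 3: hold practice constant and see what the combined table shows.** Section 9.9 says that in theory every rivaroxaban user is a switcher from parenteral treatment. Assume this is true everywhere, so the true initiator share is 0%. Let f be the share of SNDS and Swedish rivaroxaban users who switched before discharge. The documents give no value, so f runs from 0 to 1. Recorded initiators are 0% in Denmark and SIDIAP, and f in SNDS and Sweden.

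Combined initiator share = 252f/285 = 0.884f.

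If all 845 children start on a parenteral drug, rivaroxaban as the recorded index drug among all children = 252f/845.

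| f | Combined initiators (true 0%) | Rivaroxaban as index drug (true 0%) |
|---|---|---|
| 0 | 0% | 0% |
| 0.25 | 22.1% | 7.5% |
| 0.5 | 44.2% | 14.9% |
| 0.75 | 66.3% | 22.4% |
| 1 | 88.4% | 29.8% |

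**Step 4: let the hospital drug data fail to arrive.** If only SIDIAP is linked, the initiator share is 270f/285 = 0.947f. If only Denmark is available, it is 267f/285 = 0.937f. If neither is, it is f: the mixing is gone, but the misclassification remains in full.

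**The case against.** **Pooling is supplementary.** A reader might infer that two primary objectives are answered by the combined tables. The protocol does not say so. Section 9.7.1 has every analysis run separately by country and source, section 9.7.8 makes combination additional and conditional, and Table 4 rates both objectives feasible in each source. This stands and limits the damage.

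**The 88% is not the size of the mixing.** It is a ceiling, reached only if every French and Swedish child switches before discharge, and it measures missing hospital data. Section 9.9 allows that some children will not yet have switched. Mixing itself concerns the roughly 12% of rivaroxaban users from Denmark and SIDIAP. This stands too. It also rules out the stronger reading that the combined figures say nothing about practice: they would mainly show first outpatient therapy.

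**The limitation is disclosed.** Sections 9.2.3.1 and 9.9 are candid, so a misreading of the combined split as use outside the label is possible rather than likely. But the disclosure is by source and does not reach section 9.7.8.

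**The SAP may settle which variables are pooled.** Section 9.7.8 does not list them, and section 9.7.1 leaves table shells to the SAP. That is fair for detail. The index rule and the pooling criterion are fixed in the protocol, however, and the criterion considers only suppression.

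**The mix is contingent.** Annex 3 says the Danish register was not yet released for research, and Table 3 calls the SIDIAP hospital-drug linkage possible. This is true, but Table 4 counts on both.

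**Conclusion.** The point holds in a limited form. Followed as written, section 9.7.8 would let index therapy, index-episode duration, number and sequence of agents, and initiator/switcher status be combined under two definitions of the index drug. With identical on-label practice everywhere, the combined initiator share would be 0.884f instead of 0%, anywhere from 0% to 88%. It would be set by the timing of the switch relative to discharge and by the mix of sources.

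This rests on three assumptions: that the Danish register and the SIDIAP linkage both become available, that the Table 6 averages describe the mix, and that every rivaroxaban user is truly a switcher. SNDS records some costly hospital drugs (Table 3), but the protocol does not say that anticoagulants are among them.

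By-source tables remain interpretable. Demographics and later maintenance therapy are little affected.

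A reader might also infer that moving all four sources to a common outpatient index would cure the problem. It would make the definition uniform, but in-hospital switchers in Denmark and SIDIAP would then also count as initiators. If f is the same there, the combined share rises from 0.884f to f. Eligibility would change as well, because the index date anchors the 30-day VTE window and the six-month washout.

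**What to change.** Amend section 9.7.8 as follows.

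1. Combine index-dependent results only within groups of like inpatient drug capture: Denmark + SIDIAP, labelled first recorded therapy, and SNDS + Sweden, labelled first outpatient therapy. This covers index drug and class, index-episode duration, number and sequence of agents, and initiator/switcher status.
2. Draw statements on initial parenteral treatment and on true initiator/switcher status only from the inpatient-capturing sources.
3. Keep four-source pooling for variables that do not depend on the index setting. Variables measured back from the index date, such as prior hospital stay, should be checked before being placed there.
4. If wanted, add a common first-outpatient-record index as a supplementary combined analysis. State its effect on the 30-day VTE window, on the six-month washout (earlier hospital records would have to be disregarded), and on children treated only in hospital, who would drop out.

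Items 1 to 3 need no new data and no new derivation. The cost is smaller combined groups. Denmark + SIDIAP would hold about 33 rivaroxaban users (18 and 15), so splitting by status may produce cells below the limits of five and six. The by-source tables already carry that risk.

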9.8. Quality control

The study will use existing databases in different countries, which are being used widely for research. The study will be executed in line with all applicable regulations and guidelines – such as best-practice guidelines applicable to non-interventional DUS, including but not limited to the ENCePP Guide on Methodological Standards in Pharmacoepidemiology, the ENCePP Checklist for Study Protocols, and the Guidelines for Good Pharmacoepidemiology Practices of the International Society of Pharmacoepidemiology (ISPE GPP) as well as the specific Standard Operating Procedures of each contractor. All study programs, log files, and output files will be stored on a secure server. Where elements of the study are being conducted by a third party, the datasets and analytic programs will be stored according to the vendor's procedures.

9.9. Limitations of the research methods

The use of secondary data that has not been primarily collected for research purposes comes with specific limitations.

Selection bias

- All patients fulfilling eligibility criteria will be included in the study. The data sources in the different countries differ in terms of contents and expected coverage. Most have a national coverage, while SIDIAP which only covers ~75% of Catalonia is also considered representative of the Spanish population. Therefore, the selection bias is considered to be low with respect to the target countries.

Information bias

- Exposure data
 - Anticoagulation therapy is expected to be initiated during hospital stay and renewed for outpatient use. According to its indication, rivaroxaban oral suspension should be used after at least five days of initial parenteral anticoagulation treatment. Thus, in theory, all patients receiving rivaroxaban should be switchers from parenteral anticoagulant treatment. In practice, the capacity to observe the actual initial parenteral anticoagulation treatment and its duration will depend on the availability of inpatient drug data in the selected data sources. This will be feasible when

inpatient drug data is captured, e.g., in the Danish SMR (soon available, with data collected since May 2018) and in SIDIAP through linkage with hospital dispensation medication. However, inpatient drug data is not captured in SNDS and in Swedish national registers, which represents a risk of exposure underestimation. In this latter situation, the information on anticoagulation therapy and its duration will be based on outpatient prescriptions only, at a time when patients may have already, or not yet, stopped the initial parenteral anticoagulation treatment, and switched to maintenance therapy like rivaroxaban. Hence, when patients will have switched to rivaroxaban during hospital stay in an unobservable period in the data source, they will appear as initiating anticoagulation therapy with rivaroxaban, and not switchers. To avoid immeasurable time bias, the index date will be the first observed record of anticoagulation therapy in each data source, whether it occurs during inpatient stay or afterwards.

- Prescriptions may be issued but not dispensed or dispensed but not used. No information will be available to confirm if the medication is actually taken by patient. When available, dispensing data will be preferred over prescription data to minimize the risk of exposure misclassification.
 - Patients may sometimes be exposed to more than one anticoagulant agent at the same time, e.g., when converting from rivaroxaban to VKA. However, at a given time, patients will contribute time at risk to a single exposure category, either rivaroxaban or SOC. In order to test the robustness of the main exposure assumption, a sensitivity analysis will be conducted, whereby only the first treatment agent episode will be considered, with a 30-day carry-over period added at the end of the time at risk.
- Outcomes
 - The definitions of bleeding outcomes are derived from definitions used in clinical trials and require some adaptation within the limitations that exist of available data captured in secondary data sources.
 - The ability to identify bleeding events and their severity will largely depend on the granularity of ICD-9 and ICD-10 codes (diagnoses and procedures), i.e., their sensitivity and specificity in identifying the events of interest. While this type of outcome has already been assessed among adults in previous studies on most data sources, the severity of bleeding might be difficult to determine accurately. Some of the bleedings among children might be more trivial, and will be evaluated as CRNM bleeding, while major bleeding will focus on the most severe events reported during hospitalization, either based on specific bleeding sites or reported with transfusion or as cause of death. Whenever available, prior knowledge on the algorithm to identify these outcomes will be used. The evaluation of these two co-primary bleeding outcomes (major bleeding and CRNM bleeding) with mutually exclusive definitions will allow to provide results with severity grading, thus facilitating the interpretation of study findings.
 - There is a risk of misclassification of the bleeding outcomes because of the uncertainty whether the bleeding event is the actual reason for the hospitalization. It

is also possible that a bleeding occurs while the child is already hospitalized for another reason being reported as the primary diagnosis. To mitigate this risk of misclassification, two definitions will be considered for the bleeding outcomes: in the main analysis, a sensitive approach considering all appropriate bleedings reported as primary, related, or associated diagnoses will be used as the primary definition to capture all bleedings that might represent a major bleeding or a CRNM bleeding. By increasing specificity, a sensitivity analysis restricted to those bleeding events reported as *primary* diagnoses during hospitalization will inform on the robustness of study findings.

- Recurrent symptomatic VTE. Children are likely to come to a specialist/hospital for a control visit or something related to their first VTE. On this occasion they might be recorded with a diagnosis of VTE even if this does not represent a recurrent VTE event. In order to minimize this risk of misclassification, the outcome of recurrent VTE will be restricted to VTE diagnoses recorded in inpatient setting, thus excluding control visits for VTE which most likely occur in secondary outpatient care. However, a risk of misclassification remains for children hospitalized for a long period or for other reasons than the index VTE, where it might be difficult to distinguish a recurrent VTE event from the index VTE. For this reason, the use of a primary definition of VTE diagnoses, including all primary/main and secondary diagnoses codes, and a secondary more specific definition restricted to primary VTE diagnoses reported through hospitalization will allow to test the robustness of the findings.

Other limitations

- **Impact of the small sample size**

The number of available children aged under two years with VTE is expected to be very low in most data sources due to VTE being a rare event in this population. For this reason, all analyses will be descriptive and no confirmatory comparison between exposure categories will be performed.

To comply with GDPR, cell suppression is required to mitigate the risk of re-identification in most countries. Consequently, this is a major limitation for analyses in most data sources, except SNDS in France. Besides, due to the small sample size and low frequency of the safety and efficacy outcomes, it is expected that these analyses should only be feasible in the SNDS.

- **Missing data**

Some variables, e.g., daily dosage or prescription length may have missing data. Commonly used assumptions for this type of analysis will be used to approximate values. Other variables such as duration of oral or gastric feeding or bodyweight might not be captured or only partially captured in some data sources. However, these aspects are important to describe patient characteristics, but missing data will not impact overall results of this study.

